6.5 CONTRACEPTION AND RESTRICTIONS

Male Subjects with Partners of Childbearing Potential

Male subjects who are sexually active with a partner of childbearing potential must use, with their partner, a condom plus an approved method of highly effective contraception from the time of informed consent until 97 days after last study drug administration. This is based on 90 days (one cycle of spermatogenesis) plus 5 half-lives of the IP. The half-life of the RVP-001 is unknown in humans. Therefore, the duration from final dose to the last follow-up visit/phone call will be used.

The following methods are acceptable:

- Partner's use of combined (estrogen and progestogen-containing) hormonal contraception associated with inhibition of ovulation:
 - oral
 - intravaginal
 - transdermal
- Partner's use of progestogen-only hormonal contraception associated with inhibition of ovulation:
 - oral
 - injectable/implantable
 - intrauterine hormone-releasing system
- Partner's use of intrauterine device
- Vasectomized
- Partner's bilateral tubal occlusion

Males with Partners of Non-childbearing Potential

There is a significant risk of drug exposure through the ejaculate (which also applies to vasectomized males) that might be harmful to sexual partners. Therefore, even if a male is sexually active with a partner of non-childbearing potential, they will be required to use a condom from first administration of study drug until the follow-up visit/phone call.

Female Subjects of Childbearing Potential

Female subjects who are sexually active and of childbearing potential must use, with their partner, an approved method of highly effective contraception from the time of informed consent until 37 days after last study drug administration. This has been calculated based on 30 days (one female menstrual cycle) plus 5 half-lives of the study drug. The half-life of the RVP-001 is unknown in humans. Therefore, the duration from final dose to the last follow-up visit/phone will be used.

The following highly effective methods are acceptable:

- Intrauterine device
- Vasectomized partner
- Bilateral tubal occlusion

Female subjects are not required to use any of the above contraceptive methods if their sexual partner is female.

All Subjects (Male and Female Subjects of Childbearing Potential)

Alternatively, sexual abstinence is considered a highly effective method only if defined as refraining from intercourse during the entire period of risk associated with the study treatments. The reliability of sexual abstinence needs to be evaluated in relation to the duration of the clinical trial and the preferred and usual lifestyle of the subject.

Females of Non-Childbearing Potential

Female subjects who are not of childbearing potential do not need to use any methods of contraception. A woman is considered a WOCBP unless post-menopausal or permanently sterile. Permanent sterilization methods include hysterectomy, bilateral salpingectomy, and bilateral oophorectomy. A post-menopausal state is defined as no menses for 12 months without an alternative medical cause and confirmed by a FSH result of ≥40 IU/L.

6.5.1 SPERM DONATION

Male subjects should not donate sperm for the duration of the study and for 97 days after last study drug administration.

6.5.2 EGG DONATION

Female subjects should not participate in egg donation for the duration of the study and for at least 97 days after last study drug administration.

6.5.3 PREGNANCY

Subjects will be instructed that if they/their partner becomes pregnant during the study this should be reported to the investigator. The investigator should also be notified of pregnancy occurring during the study but confirmed after completion of the study. In the event that a subject/subject's partner is subsequently found to be pregnant after the subject is included in the study, then consent will be sought from the subject/partner and, if granted, any pregnancy will be followed and the status of mother and/or child(ren) will be reported to the sponsor after delivery. Any subject reporting a pregnancy during the study will be discontinued from the study treatment and every reasonable effort will be made by Quotient to follow up the pregnancy until delivery.

A pregnancy notification form and follow-up will be completed.

6.6 LIFESTYLE CONSIDERATIONS

During this study, participants are asked to abstain from:

- food containing poppy seeds during the 48 hours prior to screening and the 48 hours prior to admission until discharge from the clinical site
- food or beverages containing xanthine derivatives or xanthine-related compounds or energy drinks from 48 hours prior to the first dosing until discharge from the clinical site
- food or beverages containing grapefruit, starfruit, pomegranate, pineapple, pomelo, and blueberries from 24 hours prior to the first dosing until discharge from the clinical site
- taking part in any unaccustomed strenuous exercise from 72 hours before the screening visit and then from 72 hours prior to admission until discharge from the study
- donating blood or plasma (outside of this study) from clinical unit admission throughout the study duration and for at least 30 days following last dose of study medication

 Consumption of alcoholic products: this will be prohibited from 24 hours prior to screening and 24 hours prior to admission until discharge from the clinical unit

The additional restrictions above are not exclusion criteria; if non-compliance occurs, the sponsor will be contacted, and each deviation will be assessed on a case-by-case basis.

6.7 SCREEN FAILURES

Screen failures are defined as participants who consent to participate in the clinical trial but are not subsequently randomly assigned to the study intervention or entered in the study.

The reason(s) for the screen failure will be documented and may include demography, screen failure details, eligibility criteria, and any serious adverse event (SAE).

6.8 STRATEGIES FOR RECRUITMENT AND RETENTION

The investigator or delegated, qualified study staff member will explain and review the Institutional Review Board (IRB) approved informed consent form (ICF) with each subject. Subjects will then be given the opportunity to ask questions and will be informed of their right to withdraw from the study without prejudice. After this explanation and before any study specific procedures are performed, the subject will voluntarily sign and date the IRB approved ICF.

7 STUDY INTERVENTION

7.1 RVP-001

The clinical formulation of RVP-001 will be prepared for IV injection. At the clinical site a predetermined dose of the drug product will be drawn from the vial into a syringe affixed with a needle, for use as an IV bolus, based on the directions in the protocol.

This product is for single-use only and will not contain a preservative.

Study drug preparations, methods of administration, and final volumes will be detailed in the studyspecific pharmacy manual.

7.1.1 PLACEBO

A volume of normal saline equal to the dose volume of RVP-001 will be administered IV and followed with the appropriate volume of saline flush. Given the lack of excipients in the formulation, normal saline is an appropriate placebo. RVP-001 is clear, colorless to pale yellow solution, and has a higher viscosity than normal saline. Therefore, all drug and placebo syringes and IV tubes used for administration will be amber tinted, and a power injector will be used to administer the IV bolus and saline chase to protect blinding.

7.1.2 ADMINISTRATION OF STUDY DRUG, MEALS, AND FLUIDS

All injectables will be prepared in the laboratory and administered using amber tinted syringes and IV tubing. Power injectors will be used to standardize injection times of the bolus and the saline flush that follows. Specific details of study drug and doses to be administered are provided in Section 7.2.3 and Section 5.2, respectively. Subjects will be dosed on the morning of Day 1.

The exact time of dosing will be decided based on logistics and will be documented in Electronic Case Report Forms (eCRF). Details of the procedures adopted for maintaining the study blind during dosing are provided in Section 7.3. If appearance matching of the placebo is not possible then masking and/or unblinded dosing teams will be used to preserve the study blind. Further details of these steps will be contained in the study specific blinding plan, which will be approved prior to dosing (see also Section 7.3). For each subject, all scheduled post dose activities and assessments will be performed relative to the time of study drug administration (see Section 9.5 for further details). Reference time for all post-dose activities will be time of beginning of bolus dose injection.

A staggered dosing schedule will be used. In each cohort 2 sentinel subjects (1 active and 1 placebo) will be dosed first and the remaining 6 subjects (5 active and 1 placebo) will be dosed 24 hours later. All cohorts will be dosed in a similar manner. See Section 7.3 for further details.

To assess tolerability of the IV administration, the first subject will be dosed at least 30 min prior to dosing the second subject. All subsequent dosing of the study drug will be staggered by at least 15 min. To allow

for potential interruptions and injector variations, up to a 20% difference in duration of the infusion will not be considered as a protocol deviation provided that full planned dose is administered. Any such minor discrepancies should not have a significant impact on the overall study objectives.

The planned injection time will be approximately 5-15 sec (depending upon patient weight/dose); the actual infusion start and stop time will be recorded in the source documents. In all cases, the study drug injection will be followed by 20 second injection of normal saline.

A 20 gauge IV will be started in the right antecubital fossa, where possible, and must demonstrate easy flush. An IV bolus injection of RVP-001 will be administered via a power injector at a flow rate of up to 2 mL/sec followed by bolus administration of up to 40 cc of normal saline also administered at up to 2 mL/sec. Precise volumes and rates of injection of both RVP-001 and saline flush will be recorded.

Further details of procedures for injection can be found in the study drug injection guidelines.

IV blood samples will be obtained from the opposite arm to the bolus, where possible.

7.1.3 MEALS AND FLUID

Subjects will be allowed water up to 1 hour before the scheduled dosing time. Subjects will be required to drink 250 mL of water at 1 hour post-dose to ensure adequate hydration and an additional 250 mL of water 1-2 hours post dose. Thereafter, water will be allowed ad libitum. Subjects will be strongly encouraged to drink allowed fluids throughout study. Decaffeinated fluids will be allowed ad libitum from lunch time on the day of dosing.

The caloric/fat content of meals are not required to be controlled. Subjects will be provided with a standardized menu that does not contain foods high in Mn content.

Subjects will be provided with a light snack and then fast from all food and drink (except water) for a minimum of 8 hours prior to dosing until approximately 4 hours post-dose at which time lunch will be provided. An evening meal will be provided at approximately 10 hours post-dose and an evening snack at approximately 14 hours post-dose. On subsequent days, meals will be provided at appropriate times.

7.2 PREPARATION/HANDLING/STORAGE/ACCOUNTABILITY

7.2.1 PACKAGING, LABELING AND DISPENSING

The Sponsor will be responsible for ensuring that the study drug is manufactured in accordance with applicable current Good Manufacturing Practice (GMP) regulations and requirements.

The study drug will be labeled according to the requirements of local law and legislation. The study drug will be prepared and dispensed according to the pharmacy manual by the clinical site's pharmacy.

Based on the subject selection list, the appropriate dose of RVP-001 or matching placebo will be prepared and dispensed by an unblinded pharmacist at the clinical site.

7.2.2 STORAGE AND HANDLING

At the study site, study drug must be kept in a secure, locked area or locked cabinet with access restricted to designated study site personnel. Vials should be stored at room temperature of 25°C (77°F), excursions permitted between 15°C to 30°C (59°F to 86°F) in a dry area, protected from light. The lot numbers and expiration dates (where available) of the study drugs supplied will be recorded in the final Clinical Study Report (CSR). Records will be made of the receipt and dispensing of the study drugs supplied. At the conclusion of the study any unused study drugs will be retained by CRO, returned to the Sponsor or designee, or destroyed, as per Sponsor instructions. If no supplies remain, this fact will be documented in the pharmacy product accountability records. All study drug will be transported, received, stored, and handled strictly in accordance with the container or product label, the instructions supplied to the clinical site and its designated pharmacy, the site's standard operating procedures (SOPs), and applicable regulations. Appropriate storage temperature and transportation conditions will be maintained for the study drug from the point of manufacture until delivery to the site. The pharmacy staff will examine the shipment to verify that the study drugs were received in acceptable condition. Once inspected, the study drugs will be stored in a secure area with access restricted only to authorized staff, under physical conditions consistent with the study drug requirements. The site pharmacist or delegate is responsible for ensuring that all study drugs received at the site are inventoried and accounted for throughout the study, according to the applicable regulations and the site's SOPs. Details of the receipt, storage, dispensing, and destruction will be recorded and maintained in the pharmacy logbook by the pharmacy staff. The Sponsor will provide written instructions regarding the final disposition of the unused study treatments. Copies of the study treatment accountability records will be provided to the Sponsor at the completion of the study and will be made available for review by the Site Monitor, if applicable, during the course of the study.

7.2.3 FORMULATION, APPEARANCE, PACKAGING, AND LABELING

The Sponsor will be responsible for ensuring that the study drug is manufactured in accordance with applicable currentGMP regulations and requirements.

The study drug will be prepared and dispensed in amber syringes according to the pharmacy manual by the clinical site's pharmacy, unless the Sponsor supplies the pharmacy with prelabeled individual dosing samples.

RVP-001 drug product is provided in clear glass vials (type 1 USP) with bromobutyl rubber stoppers and aluminum flip-and-tear type seal.

7.2.4 DOSE PREPARATION

Dosing will be weight-based, with a dose chart provided in study protocols that prescribes the precise amount of RVP-001 in ML to be dispensed at each dose level. The pharmacist will draw the appropriate volume of RVP-001 into a syringe, which may require use of multiple bottles of RVP-001.

Prepared syringes may be stored at room temperature prior to dosing for up to 60 minutes. A similar volume of normal saline will be dispensed for subjects receiving placebo. All syringes and IV tubing will be amber tinted to protect blinding. Further information will be provided in the pharmacy manual.

Further information will be provided in the Pharmacy Manual.

7.3 MEASURES TO MINIMIZE BIAS: RANDOMIZATION AND BLINDING

Subjects eligible for participation will be randomized to receive either RVP-001 or the placebo immediately prior to dosing.

A subject selection list will be produced prior to dosing using the randomization schedule and will be retained in the Investigator Site File (ISF).

For all cohorts, a sentinel group of 2 subjects will be dosed ahead of the remaining subjects in each cohort. For each cohort in which sentinel dosing is or may be used, using a computer-generated randomisation schedule, the first 2 subject numbers will be allocated to active or placebo in a 1:1 ratio (i.e., 1 subject will be randomly assigned to receive RVP-001 and 1 subject will be randomly assigned to receive placebo). The remaining 6 subject numbers will be allocated to active or placebo in a 5:1 ratio (i.e., 5 subjects will be randomly assigned to receive RVP-001 and 1 subject will be randomly assigned to receive placebo).

This is a double-blind study. Subjects and the clinical personnel involved in the collection, monitoring, revision, or evaluation of AEs, personnel of the bioanalytical department, and personnel who could have an impact on the outcome of the study will be blinded with respect to the subject's treatment assignment (RVP-001 or placebo). Blinding will be maintained at least until the clinical phase of this part of the study is completed (i.e., when investigation and reporting of all AEs has been completed for all cohorts).

The randomization schedule and disclosure envelopes will be generated by an unblinded statistician at Quotient according to Quotient's SOPs. The unblinded statistician will not be involved in any decisions relating to populations for analysis prior to unblinding. Prior to database lock and unblinding, all original randomization materials, including the original final signed and dated randomization schedule, will be held by the Quality Assurance (QA) department at Quotient. The Data Sciences department will not have access to the randomization schedule before database lock and unblinding.

Interim PK parameter estimations will be performed using bioanalytical data applied with subject aliases in order to maintain the study blind.

There may be instances where interim PK data have the potential to be treatment revealing (e.g., missed blood sampling occasions). In these cases, every effort will be made by the pharmacokineticist to maintain the study blind by appropriate presentation of data to the study team. Data demonstrating extremes of exposure will always be presented, regardless of the potential to reveal the study blind. To permit selection of the dose level, individual data may be made available in full if judged necessary by the investigator or sponsor regardless of the potential to reveal study blind. Where possible this should be to a sub-group of the review committee who are responsible for dose level selection.

Designated pharmacy personnel at the clinical sites not directly involved with the clinical aspects of the trial will prepare and dispense the study medication and will be aware of the randomization code. A copy of the randomization schedule or corresponding disclosure envelopes will also be made available to the pharmacovigilance provider for analysis of pharmacovigilance.

The study drug and placebo will have the same visual appearance in order to avoid compromising the study blinding. If appearance matching of the placebo is not possible then use of masking and/or unblinded dosing teams will be used to preserve the study blind. Further details of these steps will be contained in the study specific pharmacy manual which will be approved prior to dosing.

In the event of an emergency, or replacement of subject, an envelope for each subject containing his/her treatment assignment will be available from clinical personnel involved with the preparation of the study

medication. Two sets of disclosure envelopes (i.e., sealed envelopes containing individual subject randomization details) will be provided. One set will be held in the clinical area and the other retained in the ISF.

These may be used in the event of an emergency by the investigator. Any request for information on the randomization schedule after initial issue must be made using a randomization disclosure form, except in the case of emergency unblinding, which must be recorded on the emergency unblinding form. Access to study drug assignment will be immediately available if the investigator deems it necessary to break the study blind in the interest of a subject's medical safety, in case of a medical emergency, or if warranted during scheduled safety reviews. The medical monitor must be contacted within 24 h following disclosure of study drug assignment.

Details of any disclosure of the randomization schedule will be documented and retained in the ISF. The sponsor will be notified if the study blind is broken.

The study blind will be broken after the study database has been locked and the safety population has been defined. Any subsequent request for issue of the randomization schedule prior to unblinding must be made using a randomization disclosure form.

The randomization code will not be available to the bioanalytical lab prior to the analysis of the plasma samples from each cohort.

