8.3.3 TRIAL STOPPING RULES

Dosing and/or recruitment will be interrupted until the SRC has completed a thorough review of all available data, for any of the following reasons, but not limited to:

• If 1 subject experiences an SAE

Clinical trial stopping rules:

- If 2 RVP-001 related SAEs occur in a cohort
- If 2 subjects experience severe RVP-001 related AEs
- Occurrence of an RVP-001 related AE or SAE which results in death

Relatedness to study drug will be determined by the investigator.

If the study is halted, the IRB will be notified. The study may be resumed or terminated; however, it will not be resumed until a further notice to resume the study is submitted and approved by the IRB.

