9.12.2 CRITERIA FOR DOSE DECISIONS

Cohorts will be dosed sequentially in an ascending fashion.

Following completion of each SAD cohort, a SRC will convene to review all available blinded safety, tolerability and available PK/exposure assessments up to Day 6 (120 hours) performed for each SAD cohort, and together with attempts to correlate exposure levels with observed AEs to evaluate progression to the next dose cohort.

The SRC will be comprised of the Principal Investigator at the clinical site and the Sponsor's medical personnel, at a minimum.

Criteria for Sentinel Dosing Decision(s)

For all cohorts following a sentinel design the decision to proceed with the main group will be made by the investigator, based on safety data until 24 hours post-dose of the last sentinel subject. The investigator will inform the sponsor of any safety concerns.

For additional details refer to Data Safety Monitoring Plan (DSMP).

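### Individual interim PK may reach the investigator who rates AEs, with no requirement to fix ratings first or identify later ones

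*Combined protocol and SAP*

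**What the plan says.** Section 7.3 lists the people who must not know treatment, including clinical staff who evaluate AEs. On duration it says "Blinding will be maintained at least until the clinical phase of this part of the study is completed", and explains this as the point when AE investigation and reporting is finished for all cohorts.

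On interim PK, the same section says "Interim PK parameter estimations will be performed using bioanalytical data applied with subject aliases in order to maintain the study blind". It then gives several qualifications:

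- If the data could reveal treatment, the pharmacokineticist tries to present them in a way that keeps the blind.
- Extreme exposures are always shown, even if they reveal treatment.
- For dose selection, "individual data may be made available in full if judged necessary by the investigator or sponsor regardless of the potential to reveal study blind".
- Such a release should be confined to a sub-group of the review committee if possible. The sub-group's members are not named.
- The code may also be broken at a scheduled safety review if warranted.

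Section 9.12.2 has the Safety Review Committee (SRC) review blinded safety data and available PK to Day 6, with "attempts to correlate exposure levels with observed AEs to evaluate progression to the next dose cohort". On membership: "The SRC will be comprised of the Principal Investigator at the clinical site", plus sponsor medical personnel, as a minimum. Section 8.3.3 adds: "Relatedness to study drug will be determined by the investigator".

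**The concern.** One role can ask for individual PK, sits on the committee that may receive it, and rates relatedness. Section 7.3 says AE evaluators stay blinded until the end, yet it contains a release route that does not keep the AE rater out. It also sets no order of events: ratings need not be complete before a release, and ratings made later are not marked.

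Safety is the primary objective and each cohort has only 2 placebo subjects. If the rater learns who they are, later judgements of severity and relatedness can lean towards the known treatment. Those judgements feed the AE summaries and several stopping rules. A reader of the final tables could not separate blinded ratings from unblinded ones.

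**Working it through.** The plan gives no figure for this point. The check compares the texts, with a small count of allocations.

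**1. Blinding rule against release rule**

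| Question | What the text gives |
|---|---|
| Who must stay blinded? | Staff evaluating AEs, until AE reporting ends for all cohorts (7.3) |
| Who may call for full individual data? | Investigator or sponsor (7.3) |
| Who may receive it? | A committee sub-group if possible; membership open (7.3) |
| Is the AE rater on the committee? | The Principal Investigator is (9.12.2); the investigator rates relatedness (8.3.3) |
| Must ratings be fixed first? | Not stated; AEs are to be entered in the eCRF without delay (9.10.4) |
| Is a PK release logged? | The disclosure form covers the randomization schedule; PK release is not mentioned. The sponsor is told if the blind is broken (7.3) |

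**2. What a release can reveal**

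Inputs from 7.3: the sentinel pair is 1 active and 1 placebo; the remaining six are 5 active and 1 placebo.

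- Check on the plan's totals: (1 + 5) active to (1 + 1) placebo = 6:2 = 3:1 per cohort, and 4 × 8 = 32 subjects. These agree with 6.2.
- Possible allocations per cohort under the blind: 2 × 6 = 12. The chance of guessing all 8 correctly is 1/12 = 8.3%.
- Placebo is saline (7.1.1) and the assay measures intact RVP-001 (9.2.6). Assume placebo samples fall below the LLOQ and early active samples above it. Profiles linked to subjects then leave 1 allocation, so all 8 are known.
- Partial knowledge also spreads. Identifying one sentinel fixes the other (12 to 6 allocations). Identifying the main-group placebo subject fixes all six in that group (12 to 2).

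**3. Which ratings come after a release**

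- Section 9.9 expects safety data to the follow-up contact, for at least 7 of 8 subjects, before an escalation decision. The call is on Day 8, with a window of +1 day (3.2).
- Self-reported AEs run to Day 30 (9.10.4).
- New events after a release at that decision: Day 9 to Day 30, or 30 − 9 + 1 = 22 days at most. If the call is on Day 9, this becomes 30 − 10 + 1 = 21 days. Sentinels are dosed at least 24 hours earlier, so they have fewer days left.
- Earlier events are exposed only if they are rated late or re-rated.

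**4. Which rules use relatedness**

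- They do: one related SAE in a cohort (8.3.2); two related SAEs in a cohort, two subjects with severe related AEs, or a related fatal event (8.3.3).
- They do not: any SAE (8.3.3); moderate or severe AEs in at least half the cohort, and the laboratory, vital-sign and QTcF rules (8.3.2). The half-cohort rule still depends on severity ratings.

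**The case against.** The case on the other side is substantial.

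- **Release is optional.** It depends on a judgement of need and is steered to a sub-group, which could consist of sponsor medical personnel only. This stands: unblinding of the rater is permitted, not prescribed.
- **Full data may still be aliased.** Section 7.3 does not say that aliases are removed. Aliased profiles would show which aliases received placebo, not which subjects. This stands, and it makes linkage an assumption.
- **Events during confinement come first.** They should already be in the eCRF, and later ones are self-reported after discharge. This limits the size. But prompt entry of an event does not fix its severity and relatedness ratings.
- **The analysis is descriptive.** Sections 10.2.2 and 10.2.3 specify no formal comparison of related AEs. True, but the stopping rules still use relatedness.
- **Safety outranks the blind in a first-in-human study.** This is a fair reason to keep the release route. It does not argue against fixing ratings beforehand.
- **Other documents may close the gap.** The SAP, the Data Safety Monitoring Plan (DSMP) and the blinding plan are not in the text reviewed, nor is section 11.1.7 on governance. Any of them may name the sub-group. However, the SAP need only be signed before database lock (10.1), after the escalation reviews. The blinding plan is cited for masking at dosing (7.1.2). The DSMP could supply a safeguard, but 7.3 would still need to agree with it.

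A reader might also infer that the SRC is obliged to match each subject's exposure to AEs, that aliases make this impossible, and that full release is the sole way out. The text does not support that. Section 9.12.2 speaks of attempts and of exposure levels; nothing bars showing AEs under the same aliases; and 7.3 offers managed presentation, extreme exposures and a code break as further routes.

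**Conclusion.** The concern holds in a limited form. Section 7.3 promises that AE evaluators stay blinded, but does not prevent its own PK release from unblinding the investigator who rates relatedness. The sub-group safeguard is conditional and does not exclude the rater. No text fixes ratings before release or identifies later ones.

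The worst case per release is all 8 allocations in one cohort, with new AEs from about Day 9 to Day 30 and any re-ratings then judged with knowledge of treatment. Because the SRC meets after every completed cohort, the occasion can recur.

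This rests on four assumptions: released profiles can be linked to subjects; placebo is below the LLOQ and early active samples above it; the relatedness rater is, or shares data with, the Principal Investigator; and release happens at the escalation decision.

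It is not an expected outcome. A reader might conclude that the investigator will be unblinded, or that all follow-up from Day 7 is affected. The first overlooks that release is discretionary. The second overlooks the expectation in 9.9 of safety data to the follow-up contact.

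**What to change.** Amend 7.3 and 9.12.2, and align the DSMP:

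1. Before any individual PK is released, require severity and relatedness of all AEs to date to be entered and date-stamped.
2. Record each release and its recipients. Flag AE ratings made or changed afterwards, so that related-AE summaries can be shown with and without them.
3. Have the pharmacokineticist present AEs under the same aliases as the interim PK, so that the exposure review can be attempted without naming subjects.

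Leave emergency unblinding, the display of extreme exposures and the investigator's SRC access unchanged.

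The cost is process wording, a short log, one flag in the AE data and one extra summary, all using existing roles. Ratings must be brought up to date before a release, which may take a little time. Step 3 has a limit: in a cohort of 8, an unusual AE may let the investigator who recorded it recognise the alias. Steps 1 and 2 therefore carry most of the protection.
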